6.1.1 Radiotherapy

The choice of dose/fraction as stated below is Investigator's discretion based on patient's need. Sites will need to follow institutional practice and the guidance provided in Appendix 10 (Section 10.10) for low-dose EBRT administration.

The study population consist of patients with mCRPC, BC, NSCLC or other solid tumors who have failed at least one line of prior treatment and for whom, according to the Investigator, are eligible for low-dose EBRT for at least one symptomatic or minimally symptomatic lesion (for the prevention of symptoms).

The dose levels of EBRT will be either:

- 8 Gy as a single fraction, or
- 20/25 Gy as 5 fractions given over 5 to 10 days.

The first EBRT dose fraction must be on Day 2 of Cycle 1 and the remaining dose fractions will be given between Day 3 and Day 11. The choice of one of the EBRT dose/fractions as stated above will be at the discretion of the Investigator and will be determined by the clinical requirements of the patient. A maximum of 2 sites can be irradiated concurrently in conjunction with NOX66 during Cycle 1. EBRT will be administered according to the institutional protocol.

Additional EBRT at the dose levels/fractions stated above may be given during the study. However, should additional EBRT be considered necessary during the study (Cycle 2 onwards), the Investigator should communicate this to the Medical Monitor for team acknowledgment since extra doses could impact study results.

6.2 Preparation, Handling, Storage, and Accountability

The Investigator or designee must maintain a log to confirm appropriate temperature conditions (2°C to 8°C [35.6°F to 46.4°F], away from direct light) have been maintained during transit for

all study drug received and any discrepancies are reported and resolved before use of the study drug.

Patients must be advised that during travel from the study center to their homes the study drug must be stored at 2°C to 8°C (35.6°F to 46.4°F), away from direct light, and they should avoid leaving the study drug in their vehicle on a hot day. They should also not keep the study drug on their person as the study drug will melt at body temperature. At home the study drug should be stored in the fridge and handled as little as possible upon administration to prevent melting. Further details are provided in the "Instructions for Administration of NOX66 Suppositories".

Only patients enrolled in the study will receive study drug and only authorized site staff will supply or administer study drug. All study drugs must be stored in a secure, environmentally controlled and monitored (manual or automated) area in accordance with the labeled storage conditions with access limited to the Investigator and authorized site staff.

The Investigator or designated staff (where applicable) is responsible for study drug accountability, reconciliation and record maintenance (e.g., receipt, reconciliation and final disposition records).

Further guidance and information are provided in the "Instructions for Administration of NOX66 Suppositories" document that will be provided by the Sponsor to patients and study staff.

6.3 Measures to Minimize Bias: Randomization and Blinding

This is an open-label study. Each site must submit a completed Participant Enrollment Form to the Sponsor or CRO designee for approval to patient in the study. The Sponsor's representative (Parexel) will review the information to verify that the patient meets all inclusion criteria and none of the exclusion criteria to determine if the patient is eligible for study participation. The Investigator must not prescribe or administer the study drug until the patient has completed registration and has been approved to participate in the study.

No randomization will be done for Parts 1 and 2 as patients will all receive NOX66 and EBRT treatment. Therefore, patients will be enrolled sequentially in dose cohorts of Part 1 and in parallel for Part 2.

The clinical site will be assigned a unique 4-digit number and each patient will be assigned a unique screening number after written informed consent is obtained. Each patient will have a unique identifier (6-digit number [XXXX-YY]) that combines both the site (XXXX) and screening number (YY). Participant numbers will be assigned sequentially at the clinical site.

6.4 Study Drug Compliance

NOX66 is packaged with each suppository individually sealed in plastic packaging and boxed as quantities to meet the treatment needs. The study drug is to be stored refrigerated ($2^{\circ}C$ to $8^{\circ}C$ [35.6°F to 46.4°F]).

The suppository units are packed in individually sealed PVC suppository packaging shells and boxed in appropriate quantities. Label information for the primary packaging will include, but are not limited to the study number, name of the product, lot number, route of administration and Sponsor name.

Label information for the secondary package box which contains the suppository units will include but are not limited to the Sponsor's name and address, study number, name of the product, lot number, re-assay date, storage conditions, dosage and patient identifier.

All dosages of NOX66 will be self-administered by the study patients or administered by a caregiver. A missed dose should be taken as soon as it is noted if it has not been longer than 2 hours. If the period exceeds 2 hours, the missed dose should be skipped.

When patients are dosed at the site (Days 1, 2, 6 and 14 of Cycle 1 and Day 1 of Cycles 2 and 3), they must bring the study drug received at the start of the treatment cycle to the study site and will administer the study drug under medical supervision. The date and time of each dose administered in the clinic will be recorded in the source documents, eCRF and Patient Study Drug Administration Diary for treatment compliance. The dose of study drug and study patient identification will be confirmed at the time of dosing by a member of the study site staff other than the person administering the study drug.

When NOX66 is self-administered by the patients or administered by their care giver at home (all dosing days except the mornings of Days 1, 2, 6 and 14 of Cycle 1 and Day 1 of Cycles 2 and 3), compliance with study drug will be assessed at each visit. The patient or care giver should use gloves for drug administration. Compliance will be assessed by direct questioning and counting returned unused suppositories during the site visits and documented in the source documents and eCRF. Patients will also receive a Patient Study Drug Administration Diary in which they must record details of each dosing (e.g., date and time of dosing, number of suppositories, missed doses). Deviation(s) from the prescribed dosage regimen should be recorded in the eCRF.

A record of the number of NOX66 suppositories dispensed to and taken by each patient must be maintained and reconciled with study drug and compliance records for each cycle. Actual drug

start and stop dates, including dates for drug delays and/or dose reductions will also be recorded in the eCRF.

6.5 Concomitant Therapy

Any medication (e.g., ADT [for mCRPC patients], bisphosphonates or denosumab, pain medication) or vaccine (including COVID-19 vaccine, over-the-counter or prescription medicines, vitamins, and/or herbal supplements) that the patient is receiving at the time of enrollment or receives during the study must be recorded along with:

- Reason for use.
- Dates of administration including start and end dates.
- Dosage information including dose and frequency.

The Medical Monitor should be contacted if there are any questions regarding concomitant or prior therapy.

Other concomitant medication may be considered on a case-by-case basis by the Investigator in consultation with the Medical Monitor. Please see Sections 8.2.2.4.1 and 8.2.2.4.2, respectively, for details on permitted and prohibited medications.

6.6 Dose Modification

In patients who develop significant toxicity determined to be related to NOX66 after Cycle 1, the Investigator may reduce the number of suppositories or the daily dose for the patient to remain in the study (Table 6-2).

In the first occurrence of any AE > Grade 1 due to NOX66 (excluding Grades 1 and 2 anal/perianal rash), NOX66 treatment will be put on hold until the AE resolves to Grade 1 after which dosing can be restarted with the same dose level. If the AE occurs again, NOX66 treatment should be put on hold until the AE resolves to Grade 1 after which dosing may be restarted with a lower dose, i.e., reduced number of suppositories (Table 6-3). Grades 1 and 2 anal/perianal rash should be managed with hydrocortisone cream; no treatment hold is required in these cases.

Current Dose		Dose Reduction	
Total Daily Dose	Number of Suppositories/Day	Total Daily Dose	Number of Suppositories/Day
800 mg (400 mg BID)	2	400 mg (once daily)	1*
1200 mg (600 mg BID)	2	600 mg (once daily)	1*
1600 mg (800 mg BID [2× 400 mg per administration])	4	800 mg (400 mg BID)	2
2400 mg (1200 mg BID [2 × 600 mg per administration])	4	1200 mg (600 mg BID)	2

Table 6-2Dose Modification of Study Treatment NOX66

BID = twice daily

* To be administered during evening dosing.

Event (NCI-CTCAE v5.0)	Action	
Grades 1 to 2 toxicity (all events)	Investigator judgement to continue treatment or interrupt dose (maximum 28 days), except for Day 1 of a new cycle of study treatment, as described above. Initiate optimal supportive care and causality investigation. Consider resuming at the same dose level when toxicity has resolved or is resolving with prophylactic treatment (if appropriate). If toxicity recurs on rechallenge and does not resolve in < 7 days despite optimal supportive care, consider a dose reduction.	
Grade 3 to 4 toxicity (1 st event)	Interrupt study treatment and initiate optimal supportive care and causality investigation. Maximum treatment interruption is 28 days. When toxicity has resolved or is resolving with prophylactic treatment (Grade ≤ 2 or returns to baseline), consider restarting NOX66 with reduced number of suppositories per day and prophylactic treatment (if appropriate).	
Grade 3 toxicity (recurrence of the same AE)	Interrupt study treatment and initiate optimal supportive case and causality investigation. Maximum treatment interruption is 28 days. When toxicity has resolved or is resolving (Grade ≤ 1 or returns to baseline), consider restarting NOX66 with reduced number of suppositories per day and prophylactic treatment (if appropriate). After 2 dose reductions, consider permanent discontinuation of NOX66 for Grade 3 events.	
Grade 4 toxicity (recurrence of the same AE)	Patients should permanently discontinue NOX66 treatment.	

Table 6-3Management of NOX66 Treatment-related Toxicity

AE = adverse event; NCI-CTCAE = national cancer Institute-Common Terminology Criteria for Adverse Events

If a perineal and/or anal rash develops (Grade 1 to 2), a topical hydrocortisone containing hemorrhoid cream/ointment and/or cutaneous cream should be used. For Grade 3 to 4 perineal and/or anal rash, NOX66 treatment should be delayed until the rash has resolved to Grade 1 or completely and hydrocortisone cream should be used as appropriate. NOX66 should also be

delayed if there is proctitis, rectal mucositis or an ulcer of Grade 2 or higher. Treatment may be resumed when toxicity has decreased to Grade 1. Treatment with NOX66 should also be delayed in the presence of anorectal infections and may be resumed after they are resolved. See also Section 7.1.1 for details on handling of dose delays.

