7.1.1.1 Temporary Discontinuation

Study drug administration may be stopped temporarily (up to 21 days) due to AE(s) and will be restarted after the AE resolves to Grade 1. If an AE has not resolved after this period, but the Investigator confirms there is clinical benefit for the patient to continue study participation, this period could be extended upon discussion with Medical Monitor and Sponsor. If the AE still has not resolved after this extended period, and no clinical benefit was confirmed then the patient will be discontinued from study drug.

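### Section 6.6, Table 6-3 and Section 7.1.1.1 conflict on when to hold and restart NOX66 for the same related toxicity, and nothing says which governs

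*Combined protocol and SAP*

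**What the plan says.** **Section 6.6, text.** The rule for the first related event above Grade 1, from which only low-grade rash of the anal or perianal area is exempt, is "NOX66 treatment will be put on hold until the AE resolves to Grade 1". The text then leaves the restart dose unchanged: "after which dosing can be restarted with the same dose level". Should the event come back, a second hold to Grade 1 is followed by an optional reduction: "after which dosing may be restarted with a lower dose, i.e., reduced number of suppositories (Table 6-3".

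**Table 6-3, Grades 1 to 2 row, labelled as covering all events.** "Investigator judgement to continue treatment or interrupt dose (maximum 28 days". On resumption: "Consider resuming at the same dose level when toxicity has resolved or is resolving", the latter under prophylactic treatment where appropriate. The row carries an exception: "interrupt dose (maximum 28 days), except for Day 1 of a new cycle of study treatment, as described above".

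**Table 6-3, first Grade 3 to 4 event.** Interrupt for at most 28 days, then at Grade ≤ "2 or returns to baseline), consider restarting NOX66 with reduced number of suppositories per day".

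**Table 6-3, recurrent Grade 4 event.** Permanent discontinuation.

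**Section 7.1.1.1, adverse events generally.** Dosing may stop for up to 21 days and "will be restarted after the AE resolves to Grade 1". The period can be extended after discussion if the investigator confirms benefit. No cap on the extension and no restart dose is given.

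**Evaluability for dose escalation.** A patient without a DLT must have had at least 80% of the *planned* dosing according to the notes to the Part 1 schema (Section 1.2), or of the *prescribed* dosing according to Section 7.1.2.2.

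**The concern.** The Section 6.6 text and Table 6-3 cover the same events. The text applies to any related event above Grade 1 apart from low-grade rash. The table is headed as the management of NOX66-related toxicity, and its first row takes in every Grade 2 event. An investigator who keeps dosing through a first related Grade 2 event follows the table and departs from the text.

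This matters first for patient safety: these are instructions on stopping and restarting an investigational drug that is being escalated to 2400 mg daily, twice the 1200 mg that Section 4.2 gives as the highest dose in the earlier EBRT study. Section 8 allows no waivers and Section 10.1.11 requires the protocol to be followed exactly, so about 14 sites on three continents are bound by passages that disagree. It matters second for analysis: the adverse event and exposure summaries by dose cohort would mix patients managed under different rules. In Part 1, the choice of passage could also affect who counts as evaluable for a dose decision.

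**Working it through.** The plan gives no figure to reproduce, so the check is a comparison of passages followed by one piece of arithmetic.

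**Step 1. The passages side by side**

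| Situation | 6.6 text | Table 6-3 | 7.1.1.1 |
|---|---|---|---|
| First related Grade 2: hold? | Directed | Investigator's choice | May stop |
| First related Grade 2: restart when? | Grade 1 | Resolved, or resolving under prophylaxis if appropriate | Grade 1 |
| First related Grade 3–4: restart when? | Grade 1 | Grade 2 or lower, or baseline | Grade 1 |
| First related Grade 3–4: restart dose | Can be the same level | Consider fewer suppositories | Silent |
| Recurrent Grade 4 | Lower-dose restart permitted; Grade 4 not excluded | Permanent discontinuation | Silent on recurrence |
| Longest interruption | Not stated | 28 days | 21 days, extendable, no cap |

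The first three rows are the main conflicts. The restart-dose row differs in default only, because both sides are permissive. The last two rows are points to clarify. On duration, a hold of 22 to 28 days lies within Table 6-3 but needs an agreed extension under Section 7.1.1.1, a gap of 28 − 21 = 7 days.

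**Step 2. Does any cross-reference settle it?** There are three. The recurrence sentence cites Table 6-3 without saying that the table overrides the text. The Grades 1 to 2 row refers back to an exception for the first day of a new cycle, but nothing earlier in Section 6.6 mentions one. The end of Section 6.6 sends the reader to Section 7.1.1 for dose delays without giving an order of precedence.

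**Step 3. Part 1 evaluability.** Two assumptions are needed: the hold paragraph applies in Cycle 1 (the limit to toxicity after Cycle 1 stands in the preceding dose-reduction sentence), and held doses stay in the denominator of the 80% rule.

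- Cycle 1 doses: 14 days × 2 = 28.
- Doses needed: 0.80 × 28 = 22.4, so 23; at most 28 − 23 = 5 may be missed.
- 4 missed (2 full days): 24/28 = 85.7%, evaluable.
- 5 missed: 23/28 = 82.1%, evaluable.
- 6 missed (3 full days): 22/28 = 78.6%, not evaluable.
- 6 held doses removed from the denominator: 22/22 = 100%, evaluable.
- Counted in days: 0.80 × 14 = 11.2, so 12 days are needed; 11/14 = 78.6%, not evaluable.

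Doses left from the start of a hold to the end of Day 14 are 6 from the Day 12 morning, 5 from the Day 12 evening, 4 from the Day 13 morning and 2 from the Day 14 morning. Only a hold starting at or before the Day 12 morning dose can lose six doses. For a non-DLT Grade 2 event, such a hold under the 6.6 text makes the patient non-evaluable, while continued dosing under Table 6-3 does not.

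**The case against.** The strongest defence is that the passages are linked and can mostly be obeyed together. On a first Grade 3 to 4 event, waiting for Grade 1 and then restarting on fewer suppositories breaches neither the text nor the table. The back-reference in the Grades 1 to 2 row might mean judgement in mid-cycle and the hold rule on the first day of a cycle. The specific Grade 4 row may be meant to control recurrence, and 28 days may be 21 days plus an extension. Section 7.1.1.1 is itself compatible with the table on whether to hold for Grade 2.

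Much of this stands, and it limits the point: the recurrence and duration differences are matters for clarification, and for most pairs one course of action satisfies both passages. But no passage tells sites to choose that course, and the mid-cycle reading needs a Day 1 rule that the text does not contain. The choice between a directed hold and investigator judgement for Grade 2 remains, as does the difference in restart grade for Grade 3 to 4.

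It is also fair to say that the consequences are bounded. All analyses are descriptive, dates of delays and reductions are recorded, and relative dose intensity is reported, so differing management would be visible. For NOX66 with EBRT, Section 2.3.1 names mild dry mouth, stomatitis and fatigue as possibly related, and Section 4.2 reports no DLTs. Against that, Section 2.3.1 also records a Grade 2 anemia possibly related to NOX66 monotherapy at 800 mg, so a related Grade 2 event is not merely hypothetical.

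**Conclusion.** The point holds. For a first related Grade 2 event the protocol both directs a hold and leaves it to judgement; for a first related Grade 3 or 4 event it sets two different restart grades. Neither conflict is settled elsewhere. This is an inconsistency in a safety instruction that should be fixed.

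Its frequency cannot be estimated from the documents and none is claimed. The Part 1 effect rests on the two assumptions in the working and on a non-DLT event held for three full dosing days from no later than the Day 12 morning. Where those conditions are met, the cost is a delay or an extra patient: at least 3 evaluable patients are required per cohort, and the Safety Steering Committee can enroll more at the level (Section 7.1.2.1). No effect on the DLT definition or the Part 2 endpoints is claimed, and no view is taken on which clinical rule is right.

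**What to change.** Reconcile the Section 6.6 text, Tables 6-2 and 6-3, and Sections 7.1.1 and 7.1.1.1 into one consistent set of instructions, or state which passage governs where they differ. Table 6-2 and Section 7.1.1 belong in the exercise because Section 6.6 relies on the first for reductions and points to the second for delays. In the same amendment:

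- resolve the back-reference in the Grades 1 to 2 row, which has nothing to refer to;
- say whether the hold and restart instructions apply in Cycle 1;
- say whether the recurrence sentence covers Grade 4, and how the 21-day and 28-day limits relate;
- align the *planned* and *prescribed* wording of the 80% rule in Sections 1.2 and 7.1.2.2, and state whether held doses count.

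The clinical content is for the sponsor and investigators to decide. The cost is amendment wording and site retraining, with no added assessments and no change to the planned sample size.

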6.6.1 Dose Modification of Radiotherapy

The Investigator may adjust the dose of radiotherapy based on the standard operating procedure (SOP) of the site if the patient experiences intolerance or severe toxicity to radiotherapy during the study period.

Patients who are eligible for an additional course of radiotherapy to the same or other lesion due to chronic pain or new symptomatic lesion (not related to progression) may receive an additional course of EBRT (8 Gy or 20/25 Gy given as 1 or 5 fractionated doses, respectively). If such a case occurs, it should be discussed with the Medical Monitor before administration of the additional course.

6.7 Study Drug After the End of the Study

All patients will receive NOX66 treatment from Cycle 1 until disease progression, unacceptable toxicity, withdrawal of consent, start of a new anticancer therapy, withdrawal of the patient by the Investigator or termination of the study by Sponsor. The entire study will finish when the last patient enrolled in Part 2 completes 6 months treatment. All patients receiving study drug at that time will be switched to the NOX66 compassionate access program. Those patients on the compassionate access program will continue to receive NOX66 treatment until disease progression or unacceptable toxicity. These patients will be followed until death, or the patient is lost to follow-up.

7 Discontinuation of Study Drug and Participant Discontinuation

7.1 Discontinuation of Study Drug

7.1.1 Safety Stopping Criteria:

It may be necessary for a patient to permanently discontinue (definitive discontinuation) study drug. If study drug is definitively discontinued, the patient will remain in the study to be evaluated for clinical observation and safety monitoring. See the SoA (Table 1-1 [Parts 1 and 2]) for data to be collected at the time of discontinuation of study drug and follow-up and for any further evaluations that need to be completed.

Patients may be discontinued from study drug in the following situations:

- Patient decision. The patient free to discontinue study drug at any time, without prejudice to further treatment.
- Any AE that in the opinion of the Investigator or Sponsor contraindicates dosing or meets the criteria for discontinuation.
- Recurrence of the same Grade 3 AE, even if recurrence is at a lower dose of study drug, with the exemption of localized skin reactions associated with drug administration which responds to topical corticosteroids.
- Unacceptable toxicity.
- Severe noncompliance with the protocol.
- Disease progression or unacceptable toxicity.
- Patient started alternative anticancer therapy including another investigational agent.
- Patient is lost to follow-up.

For patients with mCRPC, study drug will not be stopped due to rises in PSA alone. The Prostate Cancer Working Group 3 (PCWG-3) emphasized the importance of keeping patients on the study until radiographic or symptomatic progression, which better reflects the clinical course.

